Institution/Department : Kaohsiung Veterans General Hospital
Principal Investigator (PI) : [name]
Research Project Title : Efficacy of H2 receptor antagonist in prevention of
thienopyridine-related peptic ulcer
NCT Number : NCT02418312
Date of the document : 11 09 2018 (MM/DD/YYYY)

ABSTRACT

Background: Current U.S. guidelines recommended thienopyridine (e.g. clopidogrel) for patients who have major gastrointestinal intolerance or complications of aspirin. However, a recent study demonstrated that 12% of patients with a history of ulcer who took clopidogrel had ulcer bleeding within one year. Although proton pump inhibitor (PPI) can prevent recurrent peptic ulcer in clopidogrel users with a history of peptic ulcer, the interaction between PPIs and clopidogrel has drawn much attention recently. Several studies reported that certain PPIs could reduce clopidogrel's antiplatelet effects and increase cardiovascular events. Theses data suggested that PPIs may potentially inhibit the CYP2C19 pathway and interfere with the conversion of clopidogrel to active form. Therefore, searching for other gastroprotective agents to prevent gastrointestinal events for clopidogrel users is urgently needed in clinical practice.

Aims: To investigate the efficacy of histamine-2 receptor antagonist in the prevention of ulcer recurrence for thienopyridine users.

Methods: 228 thienopyridine (clopidogrel or ticlopidine) users with an ulcer history who do not have gastroduodenal ulcer at initial endoscopy are included. The patients will be randomly assigned to receive either (1) famotidine (40 mg before bedtime) or (2) placebo (before bedtime) for 6 months. Blood sampling for genotyping of *CYP2C19* is carried out on enrollment. Platelet aggregation tests are performed in Day 1 and Day 28. Follow-up endoscopy is carried out at the end of the 6th month and whenever severe epigastric pain, hematemesis or melena occurs. Additionally, the episodes of acute coronary syndrome and cerebral vascular accident will be carefully evaluated during the treatment period. Finally, the ulcer recurrence rate, ulcer bleeding rate, incidence of acute

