coronary syndrome and cerebral vascular accident between the treatment groups will be compared by chi-square test. Additionally, the independent factors predicting ulcer recurrence will be investigated by multivariate analysis. Furthermore, the effect of *CYP2C19* genetic polymorphism on the development of cardiovascular events and platelet aggregation will be analyzed.

INTRODUCTION

Platelet activation and aggregation play an important role in the pathogenesis of arterial thrombosis and lead to ischemic events. Thienopyridine (clopidogrel or ticlopidine) inhibits platelet function by selectively and irreversibly blocking the adenosine diphosphate (ADP) receptor on platelets, thereby affecting ADP-dependent activation of the GpIIb-IIIa complex, the major receptors for fibrinogen present on the platelet surface.^{1, 2} Alone or in association with aspirin, clopidogrel is a thienopyridine, which has successfully proved to be beneficial in the treatment of acute coronary syndrome³ and prevention of ischemic events in patients with atherosclerotic diseases.^{4,5}

The CAPRIE study showed that long-term administration of clopidogrel to patients with atherosclerotic vascular disease is more effective than aspirin in reducing the combined risk of ischemic events.⁶ Additionally, Clopidogrel induced fewer episodes of gastrointestinal bleeding than aspirin.^{6,7} The American College of Cardiology-American Heart Association guidelines therefore recommend clopidogrel as an alternative to aspirin for patients with unstable angina or non-ST-segment elevation myocardial infarction who have an aspirin intolerance.⁸

However, a recent study demonstrated that 12% of patients with a history of ulcer who took clopidogrel had ulcer bleeding within one year.⁹ Furthermore, the cumulative incidence of recurrent bleeding in clopidogrel users who had ulcer bleeding history (subjects with high gastrointestinal risk) was higher than that in patients who took aspirin plus proton pump inhibitor (PPI).¹⁰ The mechanisms leading to recurrent ulcer bleeding among patients receiving

clopidogrel are unclear. Nonetheless, an animal study revealed that platelet ADP-receptor antagonists impair the healing of gastric ulcers by suppressing the release of platelet-derived growth factors.¹¹ We therefore speculate that clopidogrel may also hinder ulcer healing and/or precipitate ulcer formation in humans.

Recently, we have proved that proton pump inhibitor can effectively prevent recurrent

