tests, receive a ten-day course of quadruple therapy consisting of esomeprazole 40 mg b.d., bismuth subcitrate 120 mg q.d.s., tetracycline 500 mg q.d.s., metronidazole 250 mg q.d.s. An additional ^{13}C urea breath test was conducted to assess the final *H pylori* status two weeks following the six-month trial for all the patients who have *H pylori* infection on recruitment. Eradication is defined as a negative result of the final urea breath test.

Blood sampling for genotyping of *CYP2C19* is carried out on enrollment. Platelet aggregation tests are performed in Day 1 and Day 28. The *CYP2C19* genotype is determined using the polymerase chain reaction-restriction fragment length polymorphism (PCR-RFLP) as previous description.^{27,28} Genotypes are classified into three groups: homogeneous extensive metabolizer (homEM; *CYP2C19**1/*CYP2C19**1); heterogeneous extensive metabolizer (hetEM; *CYP2C19**1/*CYP2C19**2 and *CYP2C19**1/*CYP2C19**3); poor metabolizer (PM; *CYP2C19**2/*CYP2C19**2, *CYP2C19**2/*CYP2C19**3, and *CYP2C19**3/*CYP2C19**3).

Detection of H pylori on recruitment

On initial endoscopy, a biopsy specimen was obtained from the greater curvature within 5 cm of the pylorus for rapid urease test. A negative CLO test was defined by the absence of a change in color after 24 hours. Additionally, one specimen taken from the greater curvature within 5 cm from the pylorus and another taken from the greater curvature of middle body were subjected to microscopic examination for *H pylori* with the use of hematoxylin and eosin stain and Warthin-Starry stain if necessary. *H pylori* was considered to be present if either one of the two tests was positive; it was considered to be absent when both tests were negative.

Follow-up

Patients are followed up as outpatients with visits every month. Upper gastrointestinal and cardiovascular symptoms are assessed at each visit. They are asked to return to the outpatient clinic if they have persistent dyspeptic symptoms (epigastric pain, fullness, nausea or vomiting) and to report to the emergency room if they have evidences of gastrointestinal bleeding (hematemesis, melena, or sudden onset of severe epigastric pain), cardiovascular events (chest pain, syncope, or

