sudden onset of severe palpitation) or cerebrovascular accidents (conscious disturbance, hemiparesis, or dysphagia). Follow-up endoscopy with biopsy for urease test is performed whenever persistent dyspepsia, severe epigastric pain, hematemesis or melena occurred and at the end of the 6th month. The endoscopists who performed follow-up endoscopy are unaware of the treatment group assignments. The events of acute coronary syndrome and cerebral vascular accidents during the study period are carefully monitored and assessed.

End points

The primary end point are the occurrence of gastric and/or duodenal ulcers, as determined by endoscopy, during the 6-month study period. An ulcer is defined as a circumscribed mucosal break at least 0.5 cm in diameter (measured using endoscopy forceps) and with a perceptible depth.^{10,12} Only events that are confirmed by the adjudication committee and that occurred during treatment are included in the analysis. Patients who do not have follow-up endoscopic examination are assumed to have had normal findings. The secondary endpoints are: (1) the occurrence of ulcer or erosion bleeding as defined according to pre-specified criteria – namely, hematemesis or melena documented by the admitting physician, with ulcers or bleeding erosions confirmed on endoscopy, or a decrease in the hemoglobin level of at least 2 g deciliter in the presence of endoscopically documented ulcers or erosions.¹⁰ An erosion is defined as a flat mucosal break of any size;¹⁰ (2) the occurrence of unstable angina defined as rest angina (angina occurring at rest and prolonged more than 20 minutes), new-onset angina (of at least the Canadian Cardiovascular Society Class III severity) and increasing angina (angina occurring more frequently, longer in duration) with ischemic changes in electrocardiogram;²⁹ (3) acute myocardial infarction defined as at least two positive results of typical chest pain, evolutionary electrocardiogram changes and evolutionary cardiac enzyme changes; (4) the occurrence of ischemic stroke defined as sudden onset of neurological deficit due to cerebral ischemia documented by computed tomography; (5) vascular death defined as death due to cardiovascular diseases or cerebrovascular accidents. Only events that are confirmed by the cardiovascular events review board are included in the analysis.

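### Patients with no follow-up endoscopy are counted as ulcer-free, which understates ulcer rates if any of them has an ulcer and generally distorts the arm comparison when missingness is unequal

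*Combined protocol and SAP*

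**What the plan says.** In the combined protocol and SAP, Patients and Methods, the End points section defines the primary outcome: "The primary end point are the occurrence of gastric and/or duodenal ulcers, as determined by endoscopy, during the 6-month study period". It adds a restriction: "Only events that are confirmed by the adjudication committee and that occurred during treatment are included in the analysis". It then gives the rule for patients with no follow-up scope: "Patients who do not have follow-up endoscopic examination are assumed to have had normal findings".

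The Follow-up section says that endoscopy is "performed whenever persistent dyspepsia, severe epigastric pain, hematemesis or melena occurred and at the end of the 6th month". The scheduled month-6 scope applies to everyone, so ulcers without symptoms are part of the end point.

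The Abstract (Methods) lists the outcomes to be compared, beginning with the ulcer recurrence rate, and ends: "coronary syndrome and cerebral vascular accident between the treatment groups will be compared by chi-square test". It does not say whether a continuity correction is used. The text supplied gives no expected missing rate, no alternative handling of missing scopes and no sensitivity analysis for the rule.

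**The concern.** The rule is a best-case single imputation that is then treated as data. Every enrolled patient has an ulcer history, and a scheduled month-6 scope is needed because symptoms alone do not find every ulcer. Symptom-triggered scopes limit the loss, but they cannot find silent ulcers or ulcers in patients who stop attending.

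Ulcer counts may be small, so a few unseen ulcers could decide the primary result. If more scopes are missing in one arm, the rule makes that arm look better than it is. It can then create a difference or hide one, and nothing planned in the supplied text would show that this had happened.

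**Working it through.** **Inputs.** From the documents: 228 patients, two arms, binary end point, chi-square test. Assumed, because the documents do not state them: 1:1 allocation (114 per arm), two-sided 5% level, the ulcer risks and missing fractions below, and equal ulcer risk in scoped and unscoped patients. The plan gives no design figure on this point to reproduce.

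**Effect on one arm.** Let *p* be the true ulcer risk, *m* the fraction unscoped and *r* the ulcer risk among the unscoped. Then scored risk = *p* − *m* × *r*. If *r* = 0 there is no bias. If *r* = *p*, scored risk = *p*(1 − *m*). Each missed ulcer lowers its arm's rate by 1/114 = 0.88 points.

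**Effect on the comparison** (P placebo, F famotidine, *r* = *p*):
- Scored difference = (*p*P − *p*F) − (*p*P × *m*P − *p*F × *m*F).
- Scored relative risk = true relative risk × (1 − *m*F)/(1 − *m*P).

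Equal missingness therefore leaves the relative risk alone and shrinks the difference. The difference is also preserved when *p* × *m* is the same in both arms. For example, 15% × 10% = 5% × 30% = 1.5%, so 15% v 5% is scored as 13.5% v 3.5%, still 10 points. Even then the relative risk moves from 0.33 to 0.33 × 0.70/0.90 = 0.26.

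**Type I error** (no true effect, exact binomial enumeration of the Pearson test, true ulcer risk 12–30%):

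| Missing in the two arms | Uncorrected | Continuity-corrected |
|---|---|---|
| 5-point gap (5/10%, 10/15%) | 5.2–5.8% | 3.0–4.1% |
| 10-point gap (5/15%, 10/20%) | 6.1–8.2% | 3.5–6.0% |
| 5/20% | 7.4–12.1% | 4.4–9.2% |

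At 15% risk with 10/30% missing, the rule gives 10.6% (7.1% corrected). Full data give 4.9% (3.1%), and complete cases (103 and 80 patients) give 5.5% (3.4%).

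**Power** (true 15% v 5%, difference 10.0 points, uncorrected test):

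| Missing P/F | Scored difference | Power under the rule | Power, complete-case |
|---|---|---|---|
| 20/20% | 12.0 − 4.0 = 8.0 | 63.6% | 63.7% |
| 10/5% | 13.5 − 4.75 = 8.75 | 66.0% | 70.7% |
| 20/5% | 12.0 − 4.75 = 7.25 | 52.9% | 68.2% |
| 5/20% | 14.25 − 4.0 = 10.25 | 80.4% | 66.6% |

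The last row shows the rule working in favour of famotidine.

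**Tipping point.** Suppose the scored result is 17 v 6 ulcers.
- Uncorrected: χ² = 228 × (17 × 108 − 97 × 6)² / (114 × 114 × 23 × 205) = 5.85, p = 0.016.
- Two unseen ulcers on famotidine and none on placebo make it 17 v 8: χ² = 228 × (17 × 106 − 97 × 8)² / (114 × 114 × 25 × 203) = 3.64, p = 0.056.
- With continuity correction one is enough. For 17 v 7, χ² = 228 × (1140 − 114)² / (114 × 114 × 24 × 204) = 3.77, p = 0.052.

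**The case against.** The strongest reply is that the harm is conditional and may be small. The documents give no missing rate and no reason to expect it to differ by arm. Both arms have the same visit and endoscopy schedule, the comparator is a placebo, and the follow-up endoscopists do not know the allocation. With balanced missingness the test hardly changes (63.6% v 63.7% power). At low ulcer risk the inflation is slight: at 5% risk, uncorrected type I error is 4.5–4.6% for a 5-point gap, 5.2% for 5/20% missing and 5.8% for 10/30%. The tipping-point example puts both unseen ulcers on famotidine, so it shows that a borderline result is fragile, not that an error is likely. The rule is also openly pre-specified and keeps every randomised patient in the denominator.

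All of this is correct, and it limits the size of the problem. It does not remove it. Pre-specification does not make an unseen outcome known, and the rule is not reliably conservative, because it favours whichever arm has more missing scopes. The plan sets no limit on missingness.

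The supplied text ends at the end points without a separate statistics section, and its reference list stops at 22 although the text cites up to 29. A sensitivity analysis may therefore exist in text not seen here. The rule itself is explicit either way.

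**Conclusion.** The concern holds. The rule understates the ulcer rates whenever an unscoped patient has an ulcer. Unless the losses happen to cancel, it distorts the arm comparison when missingness differs. This is a weakness in missing-data handling for the only primary end point; it is neither an internal contradiction nor a demonstrated bias.

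The direction cannot be known in advance. The size ranges from negligible (small gaps or low ulcer risk) to roughly double the nominal error rate (gaps of 15 to 20 points at 15% risk or more, uncorrected test). It depends on the assumed 114 per arm, the assumed ulcer and missing rates, and equal risk in scoped and unscoped patients. If the unscoped are at higher risk, the understatement is larger.

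**What to change.** Replace the sentence. A randomised patient with no confirmed ulcer and no month-6 endoscopy has a missing primary outcome. Then:

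- Base the primary estimate on a method that does not assume normal findings. One option is multiple imputation using arm and at most two predictors already collected, such as baseline *H. pylori* status and symptoms (the Follow-up section notes that "Upper gastrointestinal and cardiovascular symptoms are assessed at each visit"), with a penalised fit because ulcers may be few.
- Report missing endoscopies by arm.
- Keep the present rule and a complete-case analysis as sensitivity analyses, with a tipping-point table.

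As points of detail, state how deaths and patients whose only scope was an early normal one are classified. The endoscopy triggers in the Abstract and the Follow-up section differ and should be reconciled; the argument does not depend on either point.

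**Cost.** The interval widens. The 95% half-width is 1.96 × √[*p*P(1 − *p*P)/*n*P + *p*F(1 − *p*F)/*n*F]. At true 15% v 5% with 10% missing in both arms, it goes from 7.3 points (13.5% v 4.5%, 114 per arm) to about 8.1 (15% v 5%, 102.6 per arm). With 20% missing it goes from 7.0 (12% v 4%, 114 per arm) to about 8.6 (15% v 5%, 91.2 per arm), or up to about 8.8 allowing for imputation. Imputation rests on a missing-at-random assumption that cannot be tested, which is why the tipping-point table is needed. Programming is modest, and no new patients or procedures are required.
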